8.1 Adverse-Event Start Date Imputation

The general principle for imputing incomplete or missing AE start dates will be to assume that AEs are 16996-emergent, by imputing the start date at the earliest time in study 16996, whenever possible.

If the start date is completely missing, then the start date will be imputed using the date of informed consent to study 16996.

If the incomplete start date has day and month missing, then the following will be applied:

- If the year is same as the year of informed consent to study 16996, then the day and month of the date of informed consent to study 16996 will be assigned to the missing fields.
- If the year is prior to the year of informed consent to study 16996, then December 31 will be assigned to the missing fields.
- If the year is after the year of informed consent to study 16996, then January 01 will be assigned to the missing fields.

If the incomplete start date has missing day only, then the following will be applied:

- If the month and year are same as the year and month of informed consent to study 16996, then the date of informed consent will be assigned to the missing day.
- If the month and year are before the year and month of informed consent to study 16996, then the last day of the month will be assigned to the missing day.
- If the month and year are after the year and month of informed consent to to study 16996, then the first day of the month will be assigned to the missing day.

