##### Definition of AE

In a clinical study, an AE is any untoward medical occurrence (i.e., any unfavorable and unintended sign [including abnormal laboratory findings], symptom or disease) in a patient or clinical investigation subject after providing written informed consent for participation in the study. Therefore, an AE may or may not be temporally or causally associated with the use of a medicinal (investigational) product.

In this study, for an event to be classified as an AE, it must be considered to be related to radium-223 dichloride/placebo by the investigator, and ongoing at or occurring from the time of the signing of the ICF and the end of the study. Also classified as AEs (regardless of the investigator's causality assessment) are all occurrences of leukemia, myelodysplastic syndrome, aplastic anemia, primary bone cancer, or any other new primary malignancy; all bone fractures and bone associated events (e.g., osteoporosis) regardless of the investigator's

causality assessment; and, in subjects who receive cytotoxic chemotherapy, all occurrences of febrile neutropenia or hemorrhage.

A surgical procedure that was planned prior to the start of the study by any physician treating the subject should not be recorded as an AE (however, the condition for which the surgery is required may be an AE).

In the following definitions of AEs from the feeder trials, the term “condition” may include abnormal symptoms and diseases.

- Conditions considered to be related to radium-223 dichloride/placebo by the investigator that started before signing of informed consent and for which symptoms or treatment are present after signing of informed consent will be carried over from the feeder trial and documented as AEs.
- Conditions considered to be related to radium-223 dichloride/placebo by the investigator that started or deteriorated after signing of informed consent will be documented as AEs. This includes intercurrent illnesses considered to be related to radium-223 dichloride/placebo by the investigator.

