6.4.2 Adverse Events

Only select categories of post-treatment AEs are to be collected in the long-term follow-up study 16996, including radium-223 dichloride/placebo related AEs and SAEs. The following AE categories identified by the protocol will be evaluated separately:

- New primary malignancies, defined as leukemia, myelodysplastic syndrome, aplastic anemia, primary bone cancer, and any new primary malignancies, regardless of relationship to study drug;
- Bone fractures and bone-associated events:
- Febrile neutropenia and hemorrhage during chemotherapytreatment and for up to 6 months thereafter. A simplified analysis will be performed as specified below
- Pregnancy AEs.

In addition to the above listed select categories of post-treatment AEs collected in study 16996, events related to radium-223 dichloride/placebo by the investigator and ongoing at or occurring from the time of signing of the informed consent and the end of the study were also to be collected by the investigator.

Protocol No.: **BAY 88-8223/16996** Page: 12 of 17

For purposes of the safety analysis of this study, AEs first arising or worsening after signing the 16996 informed consent are defined as 16996-emergent AEs.

AEs will be coded according to the Medical Dictionary for Regulatory Activities (MedDRA) Version 25.1 or higher. When integrating feeder study and 16996 study data, a MedDRA version re-fresh will be performed. The MedDRA version used will be the version in effect per Bayer Standard Operating Procedures (SOPs) at the time of database lock, and will be documented in the study CSR. Differences in MedDRA versions in effect at the time of applicable lock may result in AEs being coded differently between the interim Health Authority reports and the final CSR.

The grade severity of an AE will be documented using the National Cancer Institute (NCI)-Common Terminology Criteria for Adverse Events (CTCAE, Version 4.03).

The set of MedDRA preferred terms (PTs) constituting each category of AEs for analysis purposes will be documented in an appendix to this SAP. The appendix will be approved separately from, and may be approved later than, this SAP.

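### Three AE start-date imputation rules assign the consent date without checking the stop date or carried-over status, so some pre-consent AEs can be counted as 16996-emergent

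*SAP*

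**What the plan says.** SAP 6.4.2 gives the definition: "AEs first arising or worsening after signing the 16996 informed consent are defined as 16996-emergent AEs". It does not say whether a start date equal to the consent date qualifies.

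SAP 8.1 states its principle, which is to "assume that AEs are 16996-emergent, by imputing the start date at the earliest time in study 16996, whenever possible". Seven rules follow. Three of them return the consent date:

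- Start date fully missing: "If the start date is completely missing, then the start date will be imputed using the date of informed consent to study 16996".
- Only the year known, and equal to the consent year: "then the day and month of the date of informed consent to study 16996 will be assigned to the missing fields".
- Month and year known, and equal to those of consent: "then the date of informed consent will be assigned to the missing day".

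The other four deal with a year or month known to lie before or after consent. One example is: "If the year is prior to the year of informed consent to study 16996, then December 31 will be assigned to the missing fields".

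No rule refers to the AE stop date or to whether the event came from the feeder trial. Such events do reach the 16996 data. Protocol 7.5.1.1 says that related conditions which started before consent and are still present afterwards "will be carried over from the feeder trial and documented as AEs". The listing in SAP 6.4.2.1 also covers AEs that did not emerge within 16996. SAP 5.1 limits AE analysis to data collected in 16996, and the feeder items to be integrated (SAP 5.2.1) do not include AE onset dates.

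**The concern.** Every summary in SAP 6.4.2.2 is restricted to 16996-emergent AEs. Those summaries carry the primary variables: related AEs and SAEs, new primary malignancies, fractures and bone-associated events. The emergent flag therefore decides whether an event is counted. Version 2 of the SAP removed incidence rates and cumulative incidence, so numbers and percentages of participants are what remain.

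There are two separate problems. The first is wording: the imputed date falls exactly on the boundary of the definition, and the definition does not say on which side the boundary lies. The second remains once the wording is settled. A rule that applies unconditionally can override information already in the record, namely a stop date before consent or the fact that the event was carried over. Carried-over events are related to radium-223 or placebo by definition, so over-counting from that source falls mainly on the related-AE and related-SAE summaries.

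**Working it through.** The plan gives no figure to reproduce. The check applies the seven rules of SAP 8.1 to an illustrative consent date of 15 June 2017 (an assumption) and classifies each imputed date under two readings of the definition in 6.4.2.

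| Known part of the start date | Imputed start | Strictly after consent | On or after consent |
|---|---|---|---|
| Nothing | 15 Jun 2017 | not emergent | emergent |
| Year = 2017 | 15 Jun 2017 | not emergent | emergent |
| Year = 2016 | 31 Dec 2016 | not emergent | not emergent |
| Year = 2018 | 1 Jan 2018 | emergent | emergent |
| Month = Jun 2017 | 15 Jun 2017 | not emergent | emergent |
| Month = May 2017 | 31 May 2017 | not emergent | not emergent |
| Month = Jul 2017 | 1 Jul 2017 | emergent | emergent |

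**Step 1: the four other rules.** Comparing the assigned class with every possible true onset day gives 0 errors in 366, 365, 31 and 31 days, under both readings.

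**Step 2: the two partial-date rules that return the consent date.** 15 June is day 166 of 2017, so 165 days precede it and 365 − 166 = 199 follow it.

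- Year only: the strict reading is wrong for 199/365 = 55% of possible days (later onsets dropped). The inclusive reading is wrong for 165/365 = 45% (earlier onsets counted).
- Month only: the strict reading is wrong for 15/30 = 50%, the inclusive reading for 14/30 = 47%.

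These shares apply only to AEs handled by the rule in question and give equal weight to every day. They move with the consent date: for consent on day d of a 365-day year, the year-only shares are (365 − d)/365 and (d − 1)/365.

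**Step 3: fully missing dates.** Let p be the share of such AEs that truly began before consent. The strict reading misclassifies 1 − p and the inclusive reading p. For p = 0.10 that is 90% against 10%; for 0.50, 50% against 50%; for 0.75, 25% against 75%. The documents do not give p.

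**Step 4: which reading 8.1 intends.** It sets out to treat these AEs as emergent and regards the consent date as the earliest time in the study. Only the inclusive reading achieves that.

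**Step 5: what remains under the inclusive reading.**

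- A start that is fully missing, with a stop date of 1 May 2017, is imputed to 15 June 2017. The start is then later than the stop, and the AE is flagged emergent.
- A carried-over related AE with a missing start is also given 15 June 2017 and flagged emergent, although the protocol's reason for carrying it over is that it began before consent.

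**The case against.** The strongest reply is that 8.1 openly chooses a conservative direction: when onset is unknown, count the event. That stands for onsets that really are unknown. It does not cover an event whose stop date, or whose carried-over status, already shows that it began before consent.

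Second, the cases should be few. Protocol 7.5.1.3 asks sites for start and stop dates and confines related AEs to those present at consent or arising later, so an AE that ended before consent is outside the required collection. A carried-over AE is affected only if its start is fully missing or is known only to the consent year or month, and worsening after consent would make it emergent anyway. This stands, although SAP 6.4.2.1 allows for AEs whose collection was not required.

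Third, nothing is hidden. The 6.4.2.1 listing shows the emergent flag with start and stop dates, SAP 5.4 presents partial dates as recorded, and data checks and the validity review before lock may catch a start later than its stop. That helps, but no such check is written down, and the listing does not change the tabulated counts.

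Fourth, looking up feeder AE onset dates goes beyond the limited integration declared in SAP 5.1 and 5.2.1. That is correct, so the look-up should be optional.

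A reader might also infer that all AEs imputed to the consent date drop out of the emergent tables. That needs the strict reading, which contradicts the stated aim of 8.1; it is a gap in wording and not the likely result.

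**Conclusion.** The point holds for three of the seven rules. The definition in 6.4.2 should say on or after. Under that reading the three rules can still yield a start later than the stop date, and can count a known pre-consent related AE as emergent. AEs that began on or after consent are classified correctly, so the error is always towards over-counting.

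Its size cannot be computed, because neither document gives the number of missing start dates or the share with earlier onset. The day-count shares above are illustrations under a uniform-onset assumption. Judging it uncommon rests on the collection scope in the protocol.

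Two stronger readings are not supported. One is that the imputation scheme as a whole misclassifies: four rules make no error under either reading. The other is a numerical effect drawn from the new malignancies in ALSYMPCA. With (7 + 5)/(600 + 301) = 1.33%, 800 participants would give about 10.7 events, so one event would be about 9% of the count. That shows how much any single event weighs in a small count; it says nothing about how often a date is missing or misassigned.

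**What to change.** 1. In SAP 6.4.2, define 16996-emergent as start or worsening on or after the date of consent to 16996.
2. In SAP 8.1, add that if the stop date is before consent, no start later than the stop date is imputed and the AE is classified as not emergent.
3. In SAP 8.1, add that an AE documented as carried over from the feeder trial (onset before consent) is not emergent unless it worsened after consent. Use the feeder onset date where it is readily available, as an option.
4. Keep the consent-date imputation for all other unknown dates, which preserves the conservative aim of 8.1.

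The cost is a few sentences and a small amount of programming. Items 1 and 2 need no new data. Item 3 assumes that carried-over AEs can be recognised in the 16996 records. The documents require these AEs to be documented but do not describe a marker for them, so this should be confirmed before the rule is programmed.
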